The vast majority of low back pain (with many estimates as high as 99% incidence) stems from benign musculoskeletal problems, referred to as **non-specific low back pain** (meaning that the precise cause can be difficult to determine) – the etiology being evaluated in this study. It is caused by **lumbar sprain or strain** a stretch injury to the ligaments, tendons, and/or muscles of the low back. The stretching incident results in microscopic tears of varying degrees in the soft tissues of the lower back. The injury can occur because of overuse, improper use or trauma. A diagnosis of nonspecific low back pain occurs in the absence of any serious underlying pathology or nerve root compromise.

Other etiologies of low back pain that are not being evaluated in this study include the following:

- ✓ Mechanical: Apophyseal osteoarthritis; diffuse idiopathic skeletal hyperostosis; degenerative discs; Scheuermann's kyphosis; s ("slipped disc"); thoracic or lumbar spinal stenosis;

spondylolisthesis and other congenital abnormalities; fractures; leg length difference; restricted hip motion; misaligned pelvis - pelvic obliquity; anteversion or retroversion; and abnormal foot pronation

- ✓ Inflammatory: Seronegative spondylarthritides (e.g. ankylosing spondylitis); rheumatoid arthritis; infection - epidural abscess or osteomyelitis
- ✓ Neoplastic: bone tumors (primary or metastatic); and intradural spinal tumors
- ✓ Metabolic: osteoporotic fractures; osteomalacia; ochronosis; and chondrocalcinosis.
- ✓ Psychosomatic: Tension myositis syndrome
- ✓ Paget's disease
- ✓ Referred pain: Pelvic/abdominal disease; prostate cancer; and posture
- ✓ Depression
- ✓ Oxygen deprivation

➤ Classification of low back pain

- ✓ Acute low back pain generally lasts from a few days to less than 4 weeks.
- ✓ Sub-acute low back pain lasts 4-12 weeks
- ✓ Chronic low back pain is defined as pain in the lower back region that persists for more than 3 months. It is often progressive, and the cause is typically mechanical or non-specific in nature; that is, the cause can be difficult to determine.

➤ Presentation of low back pain

Lumbar sprain strain is characterized by localized discomfort in the low back area with onset after an event that mechanically stressed the lumbar tissues. The severity of the injury can range from mild to severe, depending on the degree of strain and resulting spasm of the muscles of the low back.

➤ Diagnosis

Diagnosis of low back pain

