Medical history and physical exam can usually identify any dangerous conditions or family history that may be associated with the low back pain. Factors such as the onset, site, and severity of the pain; duration of symptoms and any limitations in movement; and history of previous episodes or any health conditions that might be related to the pain are considered. The physician will examine the back and conduct neurologic tests to determine the cause of pain and appropriate treatment. Blood tests and imaging tests may be performed to rule out more serious sources of the pain such as tumors.

Diagnostic methods available to confirm the cause of low back pain include:

- ✓ *X-ray imaging* to look for broken bones or an injured vertebra. Tissue masses such as injured muscles and ligaments or painful conditions such as a bulging disc are not visible on conventional x-rays.
- ✓ *Computerized tomography (CT)* is used when disc rupture, spinal stenosis, or damage to vertebrae is suspected as a cause of low back pain.
- ✓ *Magnetic resonance imaging (MRI)* is used to evaluate the lumbar region for bone degeneration or injury or disease in tissues and nerves, muscles, ligaments, and blood vessels.
- ✓ *Electrodiagnostic procedures* include electromyography (EMG), nerve conduction studies, and evoked potential (EP) studies to assess the electrical activity in a nerve to detect if muscle weakness results from injury or a problem with the nerves that control the muscles.

CURRENT THERAPEUTIC APPROACHES TO THE MANAGEMENT OF EPISODIC CHRONIC LOW BACK PAIN OF MUSCULOSKELETAL ORIGIN

The treatment of lumbar sprain strain centers about reducing pain and inflammation and consists of:

- ✓ *resting* the back to avoid reinjury,
- ✓ *medications* to relieve pain and muscle spasm such as *over-the-counter analgesics*, including NSAIDs (aspirin, naproxen, and ibuprofen) to reduce stiffness, swelling, and inflammation and to ease mild to moderate low back pain; *counter-irritants* applied topically to the skin as a cream or spray stimulate the nerve endings in the skin to provide feelings of warmth or cold and dull the sense of pain, and to reduce inflammation and stimulate blood flow; *anticonvulsants* which may be useful in treating certain types of nerve pain; some *antidepressants*, particularly tricyclic antidepressants such as amitriptyline and desipramine; *opioids* such as codeine, oxycodone, hydrocodone, and morphine
- ✓ *local heat* applications
- ✓ *massage*, and

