The PI will commence by presenting and reviewing in detail the items in the informed consent form with the individual and answer any questions he or she may have. To proceed, the individual must willingly sign the informed consent form.

ASSIGNMENT OF SUBJECT IDENTIFICATION NUMBER

The subject will be assigned a unique subject identification number based upon his or her order of entry into the study.

Additional information about the informed consent and subject ID number assignment is contained in a later section of the protocol titled, "SAFETY AND CONFIDENTIALITY ISSUES."

STUDY QUALIFICATION EVALUATION: INCLUSION/EXCLUSION CRITERIA

INCLUSION CRITERIA

To be eligible for study participation, a subject must satisfy each of the following criteria.

- The subject's presenting primary pain must be located in the region of the lower back, right and/or left side(s), with the 'lower back' region defined as the area between the boundaries of the lowest rib and the crease of the buttocks
- Subject's low back pain is of musculoskeletal origin, defined as low back pain stemming from benign musculoskeletal problems wherein the etiology is lumbar sprain or strain - a stretch injury to the ligaments, tendons, and/or muscles of the low back - that occurs in the absence of any serious underlying pathology or nerve root compromise

Diagnosis is based on the following subject profile information:

a) Patient History:

(i) Initial onset of low back pain occurred after one or more of the following:

- ✓ known injury, such as an accident or fall
- ✓ overexertion of a muscle, such as after unusual amounts of exercise or unaccustomed activity, or sustained positioning (typically indicative of a strain injury)
- ✓ sudden force or movement exerted upon ligaments, such as unusual turning or twisting (typically indicative of a sprain injury)

(ii) At least two of the following five are reported:

- ✓ Complaints of pain and/or loss of function such as inability to turn, twist or bend normally
- ✓ Pain located along lower back and upper buttocks; may radiate into surrounding tissue
- ✓ Pain worsens with activity

- ✓ Painful muscle spasms that can worsen with activity or at night while asleep
- ✓ History of prior back injury

(iii) Otherwise in general good health

b) Physical Examination:

At least three of the following six are reported:

- ✓ Inability/difficulty straightening into normal posture while standing

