- ✓ Particular activities, such as sitting, standing, walking, driving, are limited, difficult or impossible
- ✓ While lying in prone position, palpation of muscles in lower lumbar area reveals local tenderness and muscle spasm
- ✓ Change in sensation and/or motor function of knees and ankles
- ✓ Raising straight leg from supine position produces sciatica
- ✓ Upon observation, there is no notable posture, spinal alignment or other back deformities

c) Medication Use History: History of taking muscle relaxants or anti-inflammatory medications, either over-the-counter and/or prescription medications.

d) Records and Diagnostic Testing:

Where available, review of prior relevant medical records from the subject's primary treating physician and review of confirmatory prior diagnostic testing, such as x-ray, MRI or CAT scan reports will be conducted.

If the applicable medical records and diagnostic testing listed above are not available or have not been conducted, the study investigator will record and evaluate all applicable information and perform an x-ray, the results of which will then be reviewed and verified as consistent with the study condition before confirming study qualification.

If following the above review, a definitive diagnosis of low back pain stemming from benign musculoskeletal problems wherein the etiology is lumbar sprain or strain - a stretch injury to the ligaments, tendons, and/or muscles of the low back - that occurs in the absence of any serious underlying pathology or nerve root compromise cannot be made, or other possible etiologies of the low back pain are identified or cannot be satisfactorily ruled out, the subject will not qualify for participation in the clinical study.

- The subject's presenting low back pain is episodic chronic, defined as:
 - ongoing lower back pain having occurred over at least the preceding three months, with lower back pain having occurred on at least 15 days of each of the preceding 3 months, *and*
 - each individual episode of lower back pain over the preceding 3 months having lasted for a period of at least 24 hours followed by a subsequent period of at least 24 hours without pain
- The subject's self-reported Degree of Pain rating on the 0-100 VAS pain scale is 40 or greater

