 - ✓ *Neoplastic*: bone tumors (primary or metastatic); and intradural spinal tumors
 - ✓ *Metabolic*: osteoporotic fractures; osteomalacia; ochronosis; and chondrocalcinosis.
 - ✓ *Psychosomatic*: Tension myositis syndrome
- Non-organic pain, defined as demonstration of positive findings for three or more of the five signs in the 'Waddell's Signs of Inorganic Behavior' list indicating a non-organic or psychological component to chronic low back pain, as follows:
 - ✓ Tenderness that is superficial and widespread and/or nonanatomic tenderness (skin discomfort on light palpation or tenderness crossing over non-anatomical boundaries)
 - ✓ Simulation of pain with sham maneuvers; i.e. with axial loading and simulated rotation (eliciting pain when pressing down on the top of the patient's head or rotating the shoulders and pelvis together should not be painful).
 - ✓ Distraction, such that less pain is reported for previously positive pain tests when attention is diverted, such as when performing a distracted straight leg raise test. For example, distraction is demonstrated if the subject complains of pain on straight leg raise, but not if the examiner extends the knee with the patient seated at another time during the evaluation
 - ✓ Regional disturbances: regional weakness or non-anatomic sensory changes which deviate from accepted neuroanatomy (such as sensory loss in an entire extremity or side of the body or weakness that is non consistent and jerky; i.e. 'cogwheeling')

- ✓ Overreaction, defined as exaggerated or 'disproportionate' painful response to a stimulus that is not reproduced when the same stimulus is given later; subjective signs regarding the subject's demeanor and reaction to testing
- Known herniated disc injury
- Known osteoporosis with compression fractures
- Osteoporosis defined as both of the following:
 - ✓ a Total SCORE on the Simple Calculated Osteoporosis Risk Estimation (SCORE) screening questionnaire of > 6, and
 - ✓ DEXA T-score \leq -2.5

If total SCORE is \leq 6, then DEXA bone density scanning will not be performed as osteoporosis is not indicated and the subject will remain eligible based on this criteria to continue with study qualification evaluation.

- Congenital deformity of spine
- Current, active chronic pain disease: chronic fatigue syndrome, fibromyalgia, endometriosis, inflammatory bowel disease, interstitial cystitis.
- Cancer or treatment for cancer in the past 6 months, including tumors of the spinal cord

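### Two findings that ordinarily suggest nerve-root involvement count toward a diagnosis defined by its absence, so the eligibility text conflicts with itself and sites could classify the same subject differently

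*Combined protocol and SAP*

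**What the plan says.** The inclusion criterion on musculoskeletal origin admits only lumbar sprain or strain "that occurs in the absence of any serious underlying pathology or nerve root compromise". The background on etiologies says the same: "A diagnosis of nonspecific low back pain occurs in the absence of any serious underlying pathology or nerve root compromise". The exclusion criteria repeat the requirement.

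The criterion then states how the diagnosis is reached: "Diagnosis is based on the following subject profile information". Four parts follow: a) history, b) physical examination, c) medication history, d) records and diagnostic testing. Part b) reads "At least three of the following six are reported". Two of its six items are "Change in sensation and/or motor function of knees and ankles" and "Raising straight leg from supine position produces sciatica". The others are difficulty straightening up, limited everyday activities, lumbar tenderness and spasm on palpation, and the absence of visible postural or spinal deformity.

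Three provisions work the other way:

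- The paragraph closing the same criterion rejects a subject if a definitive diagnosis free of nerve root compromise cannot be made, or if another cause is found or cannot be adequately excluded.
- The exclusion criteria bar a list of mechanical causes, including slipped and degenerative discs, when they are diagnosed or cannot be adequately excluded.
- A separate exclusion names "Known herniated disc injury".

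Under part d), earlier records and imaging are reviewed if they exist. If they do not, the investigator takes an x-ray. The background section on diagnosis says that "painful conditions such as a bulging disc are not visible on conventional x-rays".

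**The concern.** An examination list used to establish a diagnosis should not award points for findings that speak against it. Sciatica on straight-leg raise and altered sensation or motor function at the knees and ankles ordinarily raise the question of nerve-root involvement. Here they raise the count toward a diagnosis that requires its absence, and no text treats either as a warning or as a trigger for further work-up.

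At stake is the description of the trial population. The results are meant to support a 510(k) indication for low back pain of musculoskeletal origin, and this criterion is what defines that origin. If some sites give weight to the six-item count and others to the rule-out clause, the enrolled populations can differ by site. None of the planned analyses separates subjects by these signs, so the result could not be re-read afterwards for subjects without them.

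**Working it through.** The documents give no figure on this point to reproduce, so the check is a reading of the provisions together and a count of the ways to meet part b).

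**1. Do the two items point away from the study condition?** The protocol does not label them as nerve-root signs; that is their ordinary clinical meaning. Its own text leans the same way. The background describes lumbar sprain or strain as localized low back discomfort. Among the signs of non-organic pain, the exclusion criteria list sensory changes that do not follow neuroanatomy, so a sensory change that supports inclusion is presumably one that does.

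**2. How can part b) be met?** Inputs: six items, a threshold of three, two neurological items (N) and four others (O).

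- Sets of exactly three: C(6,3) = 20.
- Using no N item: C(4,3) = 4. Using at least one: 20 − 4 = 16. Using both: C(4,1) = 4.
- All sets of three or more: 20 + 15 + 6 + 1 = 42.
- Using no N item: C(4,3) + C(4,4) = 5. Using at least one: 42 − 5 = 37. Using both: 2⁴ − 1 = 15.
- Sets with three or more O items: (4 + 1) × 4 = 20. Sets that reach three only because of an N item: 42 − 20 = 22.

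One of the four triples with both N items takes the absence of deformity as its third. That subject passes part b) with no tenderness, spasm, postural difficulty or limited activity.

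**3. Does a later step settle the matter?** For that subject the closing paragraph asks for a definitive diagnosis without nerve root compromise. The two signs are then a reason to doubt, having just been counted as support. Neither this paragraph nor the exclusion of mechanical causes says how nerve-root or disc disease is to be excluded. Where records are missing, the one required test is an x-ray, which by the protocol's own account does not show a bulging disc. The background names MRI and electrodiagnostic studies for assessing nerves; the eligibility criteria require neither. The stand-alone herniation exclusion applies only to known cases.

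**4. Is the sample size touched?** The plan's 29 per group follows from 55% versus 20%, two-sided alpha 0.05 and power 0.80: [1.96 × √(2 × 0.375 × 0.625) + 0.8416 × √(0.55 × 0.45 + 0.20 × 0.80)]² / 0.35² = 28.8, rounded up to 29. None of these inputs depends on the examination list. Whether a mixed population would move the 55% or the 20% cannot be computed from the documents.

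**The case against.** The best defence is that three of six findings do not make a subject eligible. The examination is one of four parts, the history must also show onset after injury, overexertion or sudden force, every inclusion criterion must be met, and the closing paragraph demands a definitive diagnosis. Disc disease need not be known to exclude a subject: slipped and degenerative discs are barred whenever they cannot be adequately excluded. An investigator who reads the whole criterion can turn away the subject described above. All of this stands, and it limits the conclusion to what can happen. It does not remove the conflict, because the same sign still counts both ways and no method for excluding nerve-root or disc disease is given.

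Four stronger readings are tempting, and the documents support none of them:

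- A reader might infer from 16 of 20 that most enrolled subjects would carry nerve signs, or that the rule steers enrolment toward them. The count treats all combinations alike. Item frequencies are not given, and limited activity and absence of deformity could be very common in subjects whose VAS rating is 40 or more.
- A reader might infer that sites will ignore signs they have just scored. Nothing in the documents predicts that.
- A reader might infer that the treatment comparison is biased. Randomization is stratified by site, so any admixture is expected to balance between arms.
- A reader might add that sciatica breaches the exclusion on pain location. That exclusion concerns the presenting primary pain; pain provoked by a straight-leg raise need not be that.

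**Conclusion.** The contradiction is in the current text and is certain: part b) credits two findings toward a diagnosis that the same criterion defines by the absence of what they ordinarily suggest. It follows that a subject with nerve-root or disc pain can pass part b), and that sites could reach different decisions on the same subject. It does not follow that such subjects will be enrolled in any particular number; the share is not given and cannot be derived.

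The conclusion rests on the ordinary clinical meaning of the two signs and on the absence of any instruction that they count against eligibility. Its consequence is confined to who is enrolled and how well the result supports an indication limited to musculoskeletal origin. The randomized comparison and the sample-size calculation are not affected. This should be fixed, but it does not invalidate the design.

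**What to change.** Before enrolment, reconcile the six-item list, the definition of the condition and the two rule-out clauses (the closing paragraph of the criterion and the exclusion of mechanical causes):

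- Stop scoring the two signs toward the diagnosis without nerve root compromise.
- Record them separately on the screening form, and state how each is handled under the rule-out clauses, so that every site treats them alike.
- Have the sponsor's clinicians reset the threshold for the remaining four items. Keeping the one-half proportion, two of four, would not be a safe default: absence of deformity is a normal finding, so limited activity plus that item would be enough. Whether either sign should disqualify a subject outright is also a clinical decision that the documents do not settle.

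The cost is an edit to one list and the screening form. This reconciliation does not in itself add a test. Some subjects who would have qualified through these signs may be screened out; how many cannot be estimated from the documents.

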 10. Building up a tolerance to the alcohol or drug. Tolerance is defined by the DSM-5 as “either needing to use noticeably larger amounts over time to get the desired effect or noticing less of an effect over time after repeated use of the same amount.”
 11. Experiencing withdrawal symptoms after stopping use of a substance that can be relieved by taking more of the substance. According to the DSM-V definition and criteria, key ‘withdrawal symptoms’ include: ‘anxiety, irritability, fatigue, nausea/vomiting, hand tremor or seizure in the case of alcohol.’

Evaluation for satisfaction of the DSM-V ‘substance use disorder’ criteria will be conducted both with respect to the preceding 12 month period (current abusers) and with respect to any 12-month period in the past (history of prior abuse).

- Developmental disability or cognitive impairment that in the opinion of the investigator would preclude adequate comprehension of the informed consent form and/or ability to record the necessary study measurements
- Involvement in litigation and/or receiving disability benefits related in any way to the parameters of the study

- Subject is less than 18 years of age
- Participation in a clinical study or other type of research in the past 30 days
- Subject's primary language is other than English

WASHOUT PHASE: 48 HOURS PRIOR TO COMMENCEMENT OF THE PRE-PROCEDURE EVALUATION PHASE

The pre-procedure washout phase comprises the 48-hour period immediately preceding the pre-procedure evaluation phase, beginning upon waking on the first 24-hour period.

At the start of the pre-procedure washout phase, the subject commences his or her required abstinence from use of non-study related medications and therapies for the relief of his or her low back pain and also commences the as-needed consumption of the study rescue medication for his or her low back pain that will continue through to the end of the post-procedure evaluation phase.

WASHOUT PHASE MEASURES

On each day of the two-day pre-procedure Washout Phase, the subject records the following measures, as outlined in the STUDY TEST BATTERY section above.

- Subject Daily Diary (all applicable measures)
- Visual Analog Scale (VAS) Degree of Pain Rating: recorded upon waking on each morning of the two-day pre-procedure Washout Phase

CONFIRMATION OF CONTINUED SUBJECT STUDY ELIGIBILITY

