Prior to the subject commencing the pre-procedure evaluation phase of the study, the investigator reviews the information recorded in the pre-procedure Washout Phase Subject Daily Diary and determines the average of the 2 low back pain VAS degree of pain ratings recorded by the subject during the Washout Phase. **The calculated 2-day washout phase average VAS pain rating will become the subject's Baseline VAS pain rating for the purpose of study success evaluation.**

In order for the subject to remain qualified for study participation, the following two criteria must be satisfied:

- (i) There is no information recorded in the Subject Daily Diary that would render a subject ineligible for continued study participation, such as use of unapproved medications; and
- (ii) The subject's 2-day Washout Phase average VAS score must be upheld at 40 or greater. If it is less than 40, the subject's participation in the study ends at this time.

SUBJECT RANDOMIZATION TO PROCEDURE GROUP

A fully qualified subject is randomly assigned to Procedure Group A or to Procedure Group B, following the methodology outlined above in the STUDY DESIGN section of the protocol.

PRE-PROCEDURE EVALUATION PHASE

The pre-procedure evaluation phase commences on the day following successful completion of the two-day pre-procedure Washout Phase and following confirmation of continued subject study eligibility. During the pre-procedure evaluation phase, the following is recorded as outlined in the STUDY TEST BATTERY section above.

BASELINE VARIABLES

- Baseline Low Back Pain Variables
- Prior Treatment Approaches
- Baseline Concomitant Medication and Therapy Use
- Subject Demographics

PRE-PROCEDURE OUTCOME ASSESSMENTS

- Range of Motion (ROM)
- Visual Analog Scale (VAS) Degree of Pain Rating
- Oswestry Disability Index (ODI)/Oswestry Low Back Pain Questionnaire

PROCEDURE ADMINISTRATION PHASE

The procedure administration phase is of 4 weeks duration and comprises 8 test site visits evenly spaced across the 4 weeks for procedure administrations.

PROCEDURE ADMINISTRATION PROTOCOL

- The procedure administration phase of the study will commence within one hour subsequent to completion of the pre-procedure phase.
- The procedure administration phase will extend over 4 consecutive weeks.

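### The success baseline averages VAS readings taken at about hour 0 and hour 24 of the 48-hour washout, so for therapies with no earlier stop date the first reading still reflects usual care

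*Combined protocol and SAP*

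**What the plan says.** The Washout Phase section defines a 48-hour period "immediately preceding the pre-procedure evaluation phase, beginning upon waking on the first 24-hour period". Abstinence from usual therapy and as-needed rescue use start together: "At the start of the pre-procedure washout phase, the subject commences his or her required abstinence". Under Washout Phase Measures, the VAS is "recorded upon waking on each morning of the two-day pre-procedure Washout Phase".

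The section on confirming continued eligibility then fixes the baseline: "The calculated 2-day washout phase average VAS pain rating will become" the baseline for judging study success. The same average must be 40 or more for the subject to continue. Randomisation follows. The pre-procedure evaluation phase "commences on the day following successful completion of the two-day pre-procedure Washout Phase" and has its own VAS, which does not enter that average.

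Other rules bear on what the subject has stopped by then:

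- The exclusion criteria require 7 days without paracetamol, compound or topical analgesics, with a catch-all for equivalent products. They require 7 or 30 days without listed muscle relaxants, and 30 days without narcotics or systemic corticosteroids. The analgesic, narcotic and corticosteroid periods, and the remedial periods for muscle relaxants, are counted back from the first procedure.
- The VAS description in the Study Test Battery bars pain medication for 6 hours before any required rating.
- Physical therapy, chiropractic care, acupuncture and heat or cold packs are barred during participation, but no stop date before the washout is given. Oral NSAIDs are not named in the 7-day list.

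**The concern.** A washout exists so that baseline pain is measured free of the treatment being withdrawn. Here the first of the two ratings is taken at the moment of withdrawal, so the washout contributes nothing to it. The one rating that follows the whole washout is left out.

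For a subject whose usual therapy was not stopped earlier by another rule, half of the baseline is then a usual-care value. The endpoint is measured after 4 weeks of procedures and 8 weeks of follow-up, about 12 weeks in all, on rescue medication only. If usual therapy was helping, the baseline is too low for that comparison, and a 30% fall from it is a larger fall from the subject's off-therapy pain.

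Such subjects may be common. Recruitment is open to people currently under treatment, a history of anti-inflammatory or muscle-relaxant use is part of the diagnostic profile, and the protocol's review of current treatment lists NSAIDs, heat and spinal manipulation.

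**Working it through.** **Plan's own figure.** With 55% and 20%, two-sided alpha 0.05, power 0.80, pooled variance and no continuity correction:

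n = [1.96·√(2·0.375·0.625) + 0.842·√(0.55·0.45 + 0.20·0.80)]² / 0.35² = 28.8, so 29 per group, as stated. Power at 29 by the same approximation is 0.802. The power figures below use this formula.

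**Timeline.**

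- Hour 0: waking on day 1. Abstinence starts and reading 1 is taken.
- About hour 24: waking on day 2. Reading 2 is taken.
- Hour 48 or later: the next day. Pre-procedure VAS is taken (not used for the success baseline), then the first procedure.

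**What the earlier stops cover.** If the first procedure is at hour 48, drugs under the 7-day rule have been stopped for about 168 − 48 = 120 h at reading 1, and drugs under a 30-day rule for about 720 − 48 = 672 h. Reading 1 is a usual-care value only for what those rules miss: non-drug therapies, and any drug neither listed nor counted as equivalent.

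**Size of the shift.** The documents give no on- versus off-therapy VAS difference, so d is assumed. Let B be off-therapy pain and B − d the first reading.

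- Baseline = [(B − d) + B]/2 = B − d/2
- Success cut-off = 0.7 × (B − d/2)
- True fall needed = 1 − cut-off/B

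For success rates, assume percent change is normal with SD 25 to 35 points, set so that an unaffected baseline gives 55% and 20%. With B = 60 and every subject affected:

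| d (mm) | Baseline | Cut-off | True fall needed | Success, test | Success, placebo | Difference (points) | Power, n = 29 |
|---|---|---|---|---|---|---|---|
| 0 | 60 | 42 | 30.0% | 55% | 20% | 35 | 0.80 |
| 5 | 57.5 | 40.25 | 32.9% | 50.4–51.7% | 16.9–17.7% | 33.5–33.9 | 0.785–0.790 |
| 10 | 55 | 38.5 | 35.8% | 45.7–48.4% | 14.1–15.7% | 31.6–32.7 | 0.761–0.775 |
| 20 | 50 | 35 | 41.7% | 36.7–41.8% | 9.5–12.0% | 27.1–29.8 | 0.698–0.737 |

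For d = 10, the fall needed is 37.0% at B = 50 and 35.0% at B = 70. If only half the subjects are affected by 10 mm, the difference is about 33 to 34 points and power 0.78 to 0.79.

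**The case against.** The strongest reply is that the plan already removes much of the usual therapy. The 7- and 30-day stops take out the named analgesics, muscle relaxants, narcotics and systemic corticosteroids well before hour 0, and the 6-hour rule applies to every required rating. This stands for those drugs. A reader might infer that half of every subject's baseline is an on-treatment value; the exclusion criteria do not support that. The stops do not reach non-drug therapies, and the 6-hour rule concerns medication only. Whether oral NSAIDs fall under the catch-all for equivalents cannot be settled from the text.

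A reader might also call the endpoint off-therapy. It is not: as-needed rescue medication runs from the start of washout to the end of follow-up.

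Next, the baseline is fixed before randomisation, so any understatement falls on both arms alike. This stands. The responder comparison is not biased under the null, and the ANCOVA adjusts for baseline VAS.

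A further tempting inference is that the low first reading sends home subjects whose off-therapy pain would qualify. With steady off-therapy pain V and usual therapy worth X, the screening VAS, taken before washout, needs V − X ≥ 40, so V ≥ 40 + X (45, 50 or 60 for X = 5, 10 or 20). The washout average needs only V ≥ 40 + X/2 (42.5, 45 or 50). Anyone who passes screening passes the washout check too. Day-to-day variation could still drop a subject below 40, but that is a separate matter.

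Finally, the millimetre shifts are assumed, and eligible pain is episodic, with pain-free spells of at least 24 hours. Two consecutive mornings may differ for that reason alone. This is fair: the size is unknown, though the order of events is not.

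**Conclusion.** The point holds as a matter of timing. The baseline readings are at about hours 0 and 24, none follows the full washout, and for therapies without an earlier stop date reading 1 is a usual-care value set against a rescue-only endpoint.

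The consequence is conditional and modest. If usual therapy was not helping, nothing changes. If it was worth 5, 10 or 20 mm on an assumed off-therapy pain of 60, the 30% criterion asks for a true fall of 33%, 36% or 42%. If every subject shifts by 10 mm, approximate power at 29 per group is 0.76 to 0.78 against 0.80; if fewer are affected, the loss is smaller. This treats 55% and 20% as rates for an unaffected baseline and reading 2 as fully off therapy; the documents state neither. The loss matters somewhat more than power alone suggests, because study success requires a difference of at least 35 points and 35 is exactly what is anticipated.

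The documents do not support a reading of between-arm bias under the null, or of eligible subjects lost because of usual therapy. This is a cheap improvement to the baseline definition, not a flaw that undermines the trial.

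**What to change.** Define the success baseline as the mean of two waking VAS ratings: washout day 2 (about 24 h) and the morning of the pre-procedure evaluation (about 48 h). Use that mean for the 40-or-greater check as well. Keep the day-1 waking rating as a pre-washout descriptor only. Washout length and abstinence rules stay as they are.

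The same edit can reconcile the Statistical Analysis section, where entry to the ITT set depends on a VAS recorded at the pre-procedure visit, with the baseline definition, which currently leaves that visit's VAS out.

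The cost is a short protocol change and one more waking entry in the diary, with no added visit. The drawback is that the baseline calculation, the eligibility check and the call for group assignment move to the morning of the pre-procedure visit, so a few subjects may screen-fail there instead of before it.
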